### 2.1.2. Omnipod Horizon™ ACE Pump

The Pod component of the Omnipod Horizon™ System is similar to the Omnipod® DASH ACE Pump cleared under K191679. Compared to the DASH ACE Pump (K191679), the Horizon™ ACE Pump (Pod) has additional software to optimize communication to accept inputs from the iCGM (initially the Dexcom G6) and the Horizon™ Controller. The insulin delivery mechanism and the patient and fluid contacting components are identical to the DASH Pod.

The Pod is a lightweight, self-adhesive device that the user fills with U-100 rapid-acting insulin and wears directly on their body. The Pod delivers insulin into the user's body through a small flexible tube, called a cannula, based on the commands from the compatible controller. In the Omnipod Horizon™ System, the Pod will house the MPC algorithm and communicate directly with the iCGM and the Horizon App. The algorithm commands the Pod's insulin delivery in the form of micro-boluses based on predicted glucose values. As with the cleared Omnipod® DASH System, the Pod of the Omnipod Horizon™ System will come pre-packaged in a sterile container with a fill needle and a fill syringe. **Figure 2** below is a representation of the Pod.

**Figure 2: The Pod of the Omnipod Horizon™ ACE pump**

### 2.1.3. iCGM

The third component of the Omnipod Horizon™ System is the iCGM. The Omnipod Horizon™ System will be interoperable with a compatible iCGM, currently the Dexcom G6 Continuous Glucose Monitoring System (K191450). The Omnipod Horizon™ Pod will communicate with the Dexcom G6 via Bluetooth Low Energy (BLE). Glucose values

from the Dexcom transmitter will be sent to the MPC algorithm residing on the Pod and used in insulin dosing adjustments. The glucose values from the Dexcom transmitter will be sent independently to the Dexcom App on the controller.

### **3 HORIZON™ DATA PORTAL**

Data are securely uploaded from the PDM to Insulet Cloud by cellular connection. Data are then transferred from Insulet Cloud to the Horizon Data Portal (HDP), which is a platform for data review and management. The HDP runs on an Amazon-based web server. The HDP will provide insights including but not limited to: time in range, time at each target BG, automated/manual mode comparisons, and time spent in each mode.

Investigators will have access to all uploaded data and be able to view historical trends. The HDP will function as the data management review platform for this study.

### **4 RESULTS FROM FEASIBILITY STUDIES**

The Omnipod Horizon™ System has been tested in 194 subjects across IDE G160169, G170012, G170143 yielding approximately 13,000 subject hours of hybrid closed-loop control. The study results were presented in part at ATTD 2017, 2018, ADA 2017, 2018, and 2019, and have also been published in Diabetes Technology and Therapeutics .

### **5 STUDY SUMMARY**

#### **5.1 Study Purpose**

The purpose of this study is to assess the safety and effectiveness of the Omnipod Horizon™ System in patients with type 1 diabetes.

#### **5.2 Study Design**

This is a single-arm, multi-center, prospective clinical study. A total of up to 240 subjects aged 6-70 years with type 1 diabetes will be enrolled in the study in order to obtain a minimum of 200 evaluable subjects, 100 evaluable subjects in each age cohort (Table 1: Cohorts). Subjects will be considered evaluable if they have at least 8 weeks of data during Phase 2.

[figure not shown]
Subjects will be enrolled across 12-20 clinical study sites. Subjects who have previously participated during the feasibility studies may be enrolled in the pivotal study and will be assigned a new subject identification number. Subjects who have participated in the prepivotal study may participate in the pivotal study if it has been deemed safe for their continuation in the study and will retain their prepivotal subject identification number.

The study schedule consists of the following three phases:

- 1) 14-day outpatient standard therapy phase (Phase 1)
- 2) 13-week outpatient hybrid closed-loop phase (Phase 2)
  - A subset of subjects will participate in 5-days of supervised challenges
  - Phase 2 excludes periods due to a study pause
- 3) 12-month hybrid closed-loop extension phase (Phase 3)

Note: Subjects having completed the prepivotal study may participate in this pivotal study and begin at Phase 2 since Phase 1 was completed as part of the prepivotal study and is not required to be repeated.

**Figure 2: Study Schedule Timeline**

Cohorts are defined as shown in **Table 1**:

**Table 1: Cohorts**

Cohort (Name)	Age Range	N (minimum evaluable for primary endpoint)
Adults	14-70 years	100
Children	6-13.9 years	100

Following subject screening, enrollment, and device training, subjects will commence the standard therapy phase of the study.

Current Dexcom G6 CGM users may provide data from a 14-day period within the last 30-days. The CGM data meeting the minimum criteria must be the most recent data from the last 30-days. For non-G6 users, subjects will wear a study CGM, in blinded mode, to record glucose measurements over 14-days while subjects manage their diabetes at home per their usual routine while wearing a study CGM while remaining on their current MDI or pump therapy, and sensor, if applicable, for 14-days.

After completion of Phase 1 (the standard therapy phase), subjects will be trained on the system and transition to Phase 2 (13-week hybrid closed-loop phase) initiating

treatment with the Omnipod Horizon™ System. Subjects in each cohort will participate in prescribed challenges during any consecutive 5-days of the 13-week hybrid closed-loop phase. Phase 2 will be followed by a 12-month hybrid closed-loop phase (Phase 3).

Tables 2 and 4 outline the schedule of assessments for each phase of the study.

**Table 2: Schedule of Assessments for Phase 1 and Phase 2**

Assessment Schedule	Screening	ST1	ST2	Hybrid Closed-Loop (HCL)											EW a	
	Phase 1 e				Phase 2 c											
Visit Number	1	2	3	4	5 e	6	7	8	9	10	11	12	13	UV b		
Study Day/Visit Window l	-30 to -14d HCL start	-14d to HCL start	-1d to HCL start	1	2 ±1d	3 ±1d	10 ±3d	24 ±3d	38 ±3d	52 ±3d	66 ±3d	80 ±3d	94 ±3d	N/A		
Telephone (T) or Office (O) Visit	O	O	O	O	T/O	T/O f	O									
Laboratory Assessments																
A1c	X													X		
TSH	X															
Creatinine Level	X															
Pregnancy Test	X			X			X		X				X			
Clinical Assessments																
Informed Consent	X				X g											
Medical History (including demographics)	X															
Confirm Eligibility	X				X g											
Concomitant medications	X	X h		X h	X h	X h	X h	X h	X h	X h	X h	X h	X h	X h	X h	
Average total daily insulin (~ 7 days)		X		X												
Average total basal insulin (~ 7 days)		X		X												
Average total bolus insulin (~ 7 days)		X		X												
Pump settings/MDI dosing		X		X												
Height	X													X		
Weight	X													X		
Vital signs	X						X		X					X		
Electrocardiogram d (if applicable)	X															
Adverse events		X	X	X	X h	X h	X h	X h	X h	X h	X h	X h	X h	X h	X h	

Omnipod

Horizon™ Pivotal Study Protocol V5.0

Confidential

Page | 23

Assessment Schedule	Screening	ST1	ST2	Hybrid Closed-Loop (HCL)												EW a
	Phase 1 e				Phase 2 c											
Visit Number	1	2	3	4	5 e	6	7	8	9	10	11	12	13	UV b		
Study Day/Visit Window l	-30 to -14d HCL start	-14d to HCL start	-1d to HCL start	1	2 ±1d	3 ±1d	10 ±3d	24 ±3d	38 ±3d	52 ±3d	66 ±3d	80 ±3d	94 ±3d	N/A		
Telephone (T) or Office (O) Visit	O	O	O	O	T/O	T/O f	O									
Questionnaires																
See Table 4 for specific questionnaires	X	X												X		X
Study Devices																
Training on Glucagon administration and information on treatment of hypo/hyperglycemia		X														
Horizon Data Portal initiation/discontinuation				X										X		X
Study device training		X i		X j												
Dispense/Return BG/Ketone meter, and CGM		X												X		X
QC testing of BG/Ketone meter by site		X														
CGM sensor placement (as needed throughout)		X														
Assess CGM usage and data criteria has been met		X k	X													
Dispense/Return Horizon System				X										X		X
Complaints/device deficiencies				X h	X h	X h	X h	X h	X h	X h	X h	X h	X h	X h	X h	
Device uploads				X	X	X	X	X	X	X	X	X	X	X	X	X
Data review				X	X	X	X	X	X	X	X	X	X	X	X	X

**Table 3: Schedule of Assessments for Phase 3**

Assessment Schedule	Hybrid Closed-Loop (HCL)										UV	EW
	Phase 3											
Visit Number	14	15	16	17	18	19	20	21	22	23		
Study Day/Visit Window	120 ± 5d	150 ± 5d	180 ± 5d	210 ± 5d	240 ± 5d	270 ± 5d	315 ± 5d	360 ± 5d	405 ± 5d	450 ± 5d		
Telephone (T) or Office (O) Visit	T/O f	T/O f	T/O f	T/O f	T/O f	T/O f	T/O f	T/O f	T/O f	O	T/O f	O
Laboratory Assessments												
A1C			X			X		X		X		X
Pregnancy Test			X f			X f						
Clinical Assessments												
Informed Consent						X m						
Concomitant Medications	X	X	X	X	X	X	X	X	X	X	X	X
Height										X		X
Weight										X		X
Adverse Events	X	X	X	X	X	X	X	X	X	X	X	X
Study Devices												
Return Horizon System										X		X
Complaints/Device Deficiencies	X h	X h	X h	X h	X h	X h	X h	X h	X h	X h	X h	X h
Device Uploads (BG/Ketone Meter)	X f	X f	X f	X f	X f	X f	X f	X f	X f	X		X
Data Review	X n	X n	X n	X n	X n	X n	X n	X n	X n	X n	X n	X n

Abbreviations: S=Screening; ST1=Standard Therapy Day One; HCL=Hybrid Closed-loop; EW=Early Withdrawal; QC=Quality Control Testing; UV=Unscheduled Visit

aEarly withdrawal visit will only be conducted for any subjects that started but did not complete the full study to include standard therapy and the hybrid closed-loop phase.

bUnscheduled visits will serve as extra study visits, if needed. For unscheduled visits pertaining to a study pause and recommencement, sites should follow the assessments as defined in section 9.10.

cChallenges can occur during any consecutive 5-days during Phase 2 of the hybrid closed-loop phase. A follow up telephone visit will occur the following day after the conclusion of the challenge period.

dElectrocardiogram required for subjects >50 years old or with diabetes duration >20 years

eSubjects extending into the pivotal study from the prepivotal study will initiate their participation at Visit 5 of pivotal Phase 2.

fVisits identified as "T/O" can either be conducted in person at the clinical site or over the telephone. Visits identified as "O" can only be conducted in person at the clinical site. Vital signs, device uploads/data review from the BG and Ketone meter, and pregnancy tests are not required at any visit conducted via telephone.

gPrepivotal subjects extending into pivotal will be required to reconsent. If original prepivotal screening is within 45 days prior to the start of Phase 2 in the pivotal study, subjects will not require rescreening. All subjects must reconsent prior to commencing the extension phase (Phase 3) on or before Visit 13.

hDocumentation only applicable if there are changes from previous assessment

iStudy device training for the CGM, blood glucose and ketone meters

jStudy device training for the Omnipod Horizon™ System

kSubjects deemed exempt from wearing the study CGM for 14-days will be eligible to immediately commence the hybrid closed-loop phase at Visit 4 and may skip Visit 3/ST2 (in which case, Visit 1, Visit 2/ST1 and Visit 4 may all occur on the same day)

lIn the event of overlapping visit windows, no visits occurring during Phase 2 are to occur on the same date, except for challenge visit days. It is acceptable for a challenge visit to occur on the same date as a Phase 2 visit

mSubjects continuing in the study are to be consented for both the first 6-month and the second 6-month interval of Phase 3. Consent for each interval must occur on or any time before commencing that study interval (e.g. consent for first 6-months of Phase 3 must occur on or before Visit 13, consent for second 6-months of Phase 3 must occur on or before Visit 19).

nData review for Horizon Automated Mode to occur at all visits

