## 7 SCREENING AND ELIGIBILITY

Potential subjects for this study will include individuals who have been diagnosed with type 1 diabetes for at least 6 months and are appropriate for pump therapy per investigator's assessment. Potential subjects will be selected at each clinical study site and screened accordingly. Clinical study sites will be advised to:

- Recruit subjects using insulin aspart, lispro, and glulisine also known as Humalog, Novolog, Admelog, and Apidra
- Recruit at least 20% of subjects using MDI

Every effort will be made to establish eligibility of the patient prior to enrollment. Only patients who appear to meet all eligibility criteria will be enrolled in the study. Subject eligibility will be confirmed by study staff during a screening visit at the clinical site. Blood draws will be collected as required to demonstrate study eligibility as noted below. Laboratory results within the last 6 months, with the exception of A1C, may also be used if available.

Subjects that have participated in the prepivotal study may be eligible to extend their participation into the pivotal study. The prepivotal study will be conducted in parallel to the pivotal study and will include a minimum of 36-subjects between the ages of 6-70 years participating in a standard therapy phase followed by the hybrid closed-loop phase. The prepivotal study will be conducted at up to 8 clinical study sites. The prepivotal study outpatient hybrid closed-loop phase includes 14-days of hybrid closed-loop. Prepivotal study subjects that are eligible to extend their participation into the pivotal study do not require rescreening if their original screening is within 45-days prior to Visit 5, which is their start of Phase 2 in the pivotal study. Prepivotal subjects do not need to participate in the standard therapy phase of the pivotal study since this phase was completed as part of the prepivotal study and is not required to be repeated.

### 7.1 Visit 1

**Visit 1** will be conducted in person at the clinical study site. This visit will assess eligibility and will include:

- Signing of informed consent/assent
- Review of inclusion/exclusion criteria
- Screening assessments performed following Table 2: Schedule of Assessments for Phase 1 and Phase 2

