**Table 7: CDC Guidelines for Moderate Intensity Exercise**

	Children and Adolescents	Adults	Older Adults
Moderate Intensity Activities	Brisk walking Bicycling Hiking Catching/throwing	Walking/jogging 2.5 miles per hour Bicycling Aerobics	Walking/hiking Jogging Bicycling Aerobics

Low intensity exercise is defined using the US Department of Health and Human Services Physical Activity Guidelines for Americans and includes waking non-sedentary behaviors such as walking at 2.0 miles per hour, cooking activities, or light housekeeping.

During the challenge visits, subjects will be encouraged to:

- Follow their pre-exercise management such as insulin reduction for meal boluses, consumption of snacks, or adjusting their insulin delivery settings.
- Treat themselves per their usual routine if they become hypoglycemic or hyperglycemic or have symptoms of either at any time during the exercise challenge.

Subjects will be offered a snack prior to their release from the site upon discharge.

Inability to complete the 5-days of exercise due to an injury where participation may exacerbate the condition will not be considered a protocol deviation. Ability to participate will be up to the discretion of the investigator.

## 9.2 Visit 4

**Visit 4** represents the commencement of Phase 2 (hybrid closed-loop phase) for subjects that did not participate in the prepivotal study and will be conducted in person at the clinical site on Study Day 1. All scheduled assessments will be performed according to Table 2: Schedule of Assessments for Phase 1 and Phase 2. This visit will include:

- Pregnancy test for women of childbearing potential
- Review of concomitant medications
- Average total daily insulin (approximately over the past 7 days)
- Average total daily basal insulin (approximately over the past 7 days)
- Average total daily bolus insulin (approximately over the past 7 days)
- Pump settings/MDI dosing
- Assessment of AEs
- Initiation of Horizon Data Portal monitoring
- Omnipod Horizon™ System device training conducted by trained clinical site staff
  - Subjects will be trained on operating Omnipod Horizon™ in both Manual and Automated Modes.
  - This will include first time device set-up with entry of basal profile, bolus calculator settings with insulin:carbohydrate ratio, target glucose and correction factor.

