- Complaints/device deficiencies such as occlusion alarms and system hazard alarms since last visit
- Device uploads for BG and ketone meter for subjects extending their participation from prepivotal and the visit was conducted in the office
- Data review of Automated Mode use by clinician

#### 9.4 Visit 6

**Visit 6** will be conducted either over the telephone or in person at the clinical study site on Study Day 3 ± 1 day. This visit will include:

- Review of concomitant medications
- Assessment of AEs since last visit
- Complaints/device deficiencies such as occlusion alarms and system hazard alarms since last visit
- Data review of Automated Mode use by clinician

#### 9.5 Visit 7

**Visit 7** will be conducted either over the telephone or in person at the clinical study site on Study Day 10 ± 3-days. This visit will include:

- A pregnancy test for women of childbearing potential (if visit is conducted in person at the clinical study site)
- Review of concomitant medications
- Assessment of vital signs (if visit is conducted in person at the clinical study site)
- Assessment of AEs since last visit
- Complaints/device deficiencies such as occlusion alarms and system hazard alarms since last visit
- Device uploads for BG and ketone meter (if visit is conducted in person at the clinical study site)
- Data review of Automated Mode use by clinician

#### 9.6 Visit 8

**Visit 8** will be conducted either over the telephone or in person at the clinical study site on Study Day 24 ± 3-days. This visit will include:

- Review of concomitant medications
- Assessment of AEs since last visit
- Complaints/device deficiencies such as occlusion alarms and system hazard alarms since last visit
- Data review of Automated Mode use by clinician

#### 9.7 Visit 9

**Visit 9** will be conducted either over the telephone or in person at the clinical study site on study day 38 ± 3-days. This visit will include:

- A pregnancy test for women of childbearing potential (if visit is conducted in person at the clinical site).
- Review of concomitant medications
- Assessment of vital signs (if visit is conducted in person at the clinical site)
- Assessment of AEs since last visit

- Complaints/device deficiencies such as occlusion alarms and system hazard alarms since last visit
- Device uploads for BG and ketone meter (if visit is conducted in person at the clinical site)
- Data review of Automated Mode use by clinician

## 9.8 Visits 10, 11 and 12

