### **9.11 Recommencing After a Pause**

The commencement visit or visits may be conducted either over the telephone or in person at the clinical study site preferably within 5 business days of recommencing Phase 2 of the study. The assessments required prior to the commencement of Phase 2 will include:

- Informed consent (may be conducted over telephone or email and will contain language for the study commencement and the extension phase)
- Optional A1C (blood draw sent to NGSP laboratory)
- Pregnancy test for women of childbearing potential. If subject is not able to attend in person, they may conduct the test at home and report result to the site.
- Review of concomitant medications
- Average total daily insulin (approximately over the past 7 days)
- Average total daily basal insulin (approximately over the past 7 days)
- Average total daily bolus insulin (approximately over the past 7 days)
- Assessment of AEs
- Return Horizon System to subject (if applicable)
- Update of PDM software by the study site or provide subject with a new, updated PDM
- Resume Phase 2 of hybrid closed-loop including the following (as applicable):
  - Entry of Dexcom Transmitter ID into Horizon™ PDM
  - Initiation of Horizon™ Data Portal monitoring
  - Removal of the subject's personal insulin pump
- Complaints/device deficiencies for study devices
- Device uploads for BG and ketone meter (if visit is conducted in person at the clinical site)
- Data review by clinician will include therapy during the pause

All subjects will resume the study where they left off with respect to the visit schedule. For example, a subject that started Phase 2 (of hybrid closed-loop) on 01 February

2020, completed Visit 8 on 24 February 2020 and paused participation on 28 February 2020 has completed 28 days of Phase 2 participation. If the subject resumes Phase 2 on 01 May 2020, this date is equivalent to Day 29 of Phase 2 participation. The next scheduled study visit would be Visit 9 that should occur on Study Day  $38 \pm 3$  days. In this example, Visit 9 should occur between the 7 May and 13 May 2020, inclusive, with the optimal date being 10 May 2020. All subsequent visits will occur as scheduled.

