## 12.7 Stopping Criteria

### 12.7.1 Participant Discontinuation of Study Participation

In the case of a UADE, the Medical Monitor will determine if the use of the study device will be suspended while the problem is diagnosed. The use of the study device may continue if the Medical Monitor believes the event is explainable, unlikely to reoccur and that it is safe for the subject to continue using the device. Alternately, the Medical Monitor may request the study subject, or all study subjects, to stop using the study device or to only use in Manual Mode. Should all study subjects be required to stop using the study device or to only use in Manual Mode due an UADE, use of the study device or Automated Mode will not be restarted until approval is received from the IRB, DSMB and FDA.

Use of the study device by a participant will be discontinued if any of the following occur:

- The investigator believes it is unsafe for the participant to continue on the intervention. This could be due to the development of a new medical condition or worsening of an existing condition; or participant behavior contrary to the indications for use of the device that imposes on the participant's safety.
- The participant requests that the treatment be stopped
- Participant pregnancy
- Two distinct episodes of DKA as defined above
- Two distinct severe hypoglycemia events as defined above
- One episode of DKA and one severe hypoglycemia event as defined above

An additional requirement for continued study device use following a single DKA or severe hypoglycemia event will be that (1) the site investigator believes that the event is explainable, unlikely to recur, and that it is safe for the participant to continue to use the system and (2) the Medical Monitor concurs. If the Medical Monitor determines that the occurrence of the event indicates that it is not safe for the participant to continue to use the system, use will be discontinued, and the subject will be withdrawn from the study.

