## 13 STATISTICAL CONSIDERATIONS

### 13.1 Definition of Phase 2 and Phase 2 Participation

For the majority of subjects, Phase 2 of hybrid closed-loop data will include both data collected prior to a study pause and data collected after the recommencement. Unless otherwise specified, any data that may have been collected during a study pause (including but not limited to CGM readings from the Horizon system while in Manual Mode), will be excluded from analyses.

Continuous Phase 2 participation refers to the length of time on the Horizon system (either in Automated or Manual Modes) and is calculated as:

- Commencement of Phase 2 until a study pause (for subjects who started Phase 2 prior to a study pause)
- Recommencement until discontinuation from the Horizon system or end of Phase 2 (for subjects who started Phase 2 prior to a study pause)
- Commencement of Phase 2 until discontinuation from the Horizon system or end of Phase 2 (for subjects who started Phase 2 after a study pause)

If a subject has  $\geq 6$  weeks on the Horizon system during Phase 2 prior to a study pause and  $\geq 6$  weeks on the Horizon system during Phase 2 after the recommencement, the longer interval will be used for analysis of A1C. Specifically, the A1C associated with the longer interval, if available, will be used for the analysis of the A1C endpoints.

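### Pregnancy stops device use, yet every pregnancy test scheduled after Day 1 is waived at a telephone visit; the home test already accepted in section 9.11 is a cheap remedy

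*Protocol*

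**What the plan says.** **Stopping rule.** Protocol section 12.7.1 lists the events on which a participant's use of the device must end. "Participant pregnancy" is one of them.

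**Schedule.** Tables 2 and 3 place pregnancy tests at screening, Visit 4 (Day 1, in person), and Visits 7, 9, 13, 16 and 19 (Days 10, 38, 94, 180 and 270). Visits 20 to 23 list none. Device use continues to Visit 23 on Day 450.

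**Waiver.** Sections 9.5, 9.7, 9.9, 10.3 and 10.5 allow each of the five later visits to be by telephone and make the test conditional on attendance. Footnote f gives the general rule: "pregnancy tests are not required at any visit conducted via telephone". It also waives vital signs and meter uploads, but not A1C.

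**Home test.** Section 9.11 requires a test before Phase 2 resumes after a pause, and adds: "If subject is not able to attend in person, they may conduct the test at home and report result to the site".

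**Prepivotal subjects.** Visit 4 "represents the commencement of Phase 2 (hybrid closed-loop phase) for subjects that did not participate in the prepivotal study"; prepivotal subjects join at Visit 5 instead. Section 9.3 lists consent and confirmation of eligibility for them at that visit, but no pregnancy test. Section 7 says that they "do not require rescreening if their original screening is within 45-days prior to Visit 5".

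The SAP does not address pregnancy testing.

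**The concern.** A rule that stops the device on pregnancy can act only once the pregnancy is known. For a woman seen by telephone after Day 1, the plan requires no scheduled test that would reveal it, apart from the one on resuming after a pause. Detection then depends on her noticing the pregnancy and telling the site. What is at stake is a possible delay in applying a mandatory safety rule.

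The waiver is also stricter about attendance than the protocol is elsewhere. At recommencement, section 9.11 takes a self-reported home result as good enough for a woman about to go back on the same device. At the scheduled telephone visits the test is simply dropped.

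**Working it through.** The plan states no figure to reproduce. The check is subtraction of nominal study days.

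**Inputs.** Test days 1, 10, 38, 94, 180 and 270, and end of device use on Day 450 (Tables 2 and 3; sections 9.2, 9.5, 9.7, 9.9, 10.3, 10.5 and 10.9).

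**1. Every visit in person.** The intervals are 10 − 1 = 9, 38 − 10 = 28, 94 − 38 = 56, 180 − 94 = 86 and 270 − 180 = 90, then 450 − 270 = 180 days with no test. With the ±5-day windows at both ends, the last interval is 170 to 190 days.

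**2. Visits by telephone, current rule.** Interval from the last required test to Day 450:

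| By telephone | Last required test | Days to Day 450 |
|---|---|---|
| Visit 19 | Visit 16, Day 180 | 450 − 180 = 270 |
| Visits 16 and 19 | Visit 13, Day 94 | 450 − 94 = 356 |
| All five, no pause | Visit 4, Day 1 | 450 − 1 = 449 |

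**3. Effect of a pause.** Section 13.1 says: "For the majority of subjects, Phase 2 of hybrid closed-loop data will include both data collected prior to a study pause", together with data from after it. So the no-pause row is not the usual case. A woman who paused has one further required test, on resuming. In the section 9.11 example she resumes on 1 May, and "this date is equivalent to Day 29 of Phase 2 participation". With every later visit by telephone, 450 − 29 = 421 study days follow. Resuming at Day 2 gives 448, and at Day 94 gives 356. The 270 and 356 rows of the table do not depend on whether she paused, because the pause falls in Phase 2 and the last required test comes at or after its end.

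**4. Prepivotal entrants.** Visit 7 is their first test scheduled in this study. The prepivotal study's own tests are not in the documents. Assume none was done after a prepivotal screening 45 days before Visit 5 (nominal Day 2). The interval to Visit 7 is then 45 + 8 = 53 days, and to Visit 9 it is 45 + 36 = 81 days. Any later prepivotal test shortens both.

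**5. Home tests at Visits 9, 13, 16 and 19.** For a standard entrant whose Visit 7 test is waived, the intervals are 37, 56, 86, 90 and 180 days. The longest is 180.

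**6. The same, plus a test at Visit 21 (Day 360).** The intervals are 37, 56, 86, 90, 90 and 90 days. The longest is 90.

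Steps 5 and 6 separate two issues. Home testing repairs the telephone waiver, but leaves the 180 days after Visit 19 as they were. Only a new test time shortens those.

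**The case against.** The case for leaving the plan alone has real content.

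- **Risk is already lowered.** Exclusion 17 requires acceptable contraception at entry. Phase 3 contacts are 26 to 45 days apart, with adverse events and medications reviewed each time. Sections 9.10 and 10.10 let the investigator add assessments. Prepivotal subjects have eligibility confirmed at Visit 5. All of this stands, but none of it is a scheduled test.
- **Telephone visits need not be contact-free.** A1C is listed at Visits 13, 16, 19 and 21 with no in-person condition. That is true, although the documents do not say how the sample is taken at a telephone visit. It also means that a kit would add little burden at those visits.
- **No specific harm is shown.** Section 12.1 names no pregnancy or fetal risk of the device, and no harm from delayed discontinuation is quantified. This limits the point to an optional one.

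Some stronger readings are tempting but not supported:

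- A reader might infer that section 12.7.1 and footnote f conflict. They do not. The waiver is stated consistently, and the stopping rule does not promise any testing frequency.
- A reader might take 449 days as typical. It needs all five visits by telephone and no pause, whereas section 13.1 indicates that most subjects paused.
- A reader might suppose that home tests close the gap from Day 270 to Day 450. They leave it at 180 days.
- A reader might infer that testing ends at Visit 19 because Phase 3 was once shorter, since SAP section 2.3 describes a 6-month extension. That is possible, but the documents give no reason for the stop.

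**Conclusion.** The point holds as an optional safety improvement. All five pregnancy tests scheduled after Day 1 can be waived, so a mandatory stopping rule may have no required test behind it for 270 days (Visit 19 by telephone) or 356 days (Visits 16 and 19). The no-pause extreme is 449 study days. These are conditional figures on nominal visit days. The documents give neither the frequency of telephone visits nor the number of women of childbearing potential, so no expected gap can be stated. Separately, 180 days follow the last scheduled test even when every visit is in person. The gain from acting is modest. Endpoints, power and alpha are unaffected.

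**What to change.** **Telephone waiver.** Amend footnote f, and the in-person condition on the pregnancy test at Visits 9, 13, 16 and 19, so that at a telephone visit the woman tests at home and reports the result to the site, as in section 9.11. Do the same at Visit 7 for prepivotal entrants only; standard entrants were tested 9 days before. Keep the waiver for vital signs and meter uploads. The action on a positive result stays as in section 12.7.1.

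**After Visit 19.** This needs its own change: add a test at Visit 21 (Table 3 and section 10.7), by home kit if the visit is by telephone. An A1C sample is already due then.

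**Cost.** Protocol wording and kits, with no new visit. Each woman needs at most four kits, or five with Visit 21, plus one at Visit 7 for a prepivotal entrant. As an illustration only, assuming 25 to 60 women of childbearing potential and all these visits by telephone: 4 × 25 = 100 to 4 × 60 = 240 kits, or 5 × 25 = 125 to 5 × 60 = 300 with Visit 21, before any Visit 7 kits. The downside is the kit cost and reliance on self-reported results, which section 9.11 already accepts.
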